#### **Methods:**

### Screening Visit

Following recruitment and informed consent, subjects will undergo a screening visit that includes a physical exam, medical history, medication review, and measurement of spirometry. Subjects will be allowed to continue all of their home medications during the study, but will be asked to withhold hypertonic saline, dornase alfa, and long-acting bronchodilators for 12 hours before mucociliary clearance (MCC) scans. No bronchodilators will be given.

### Randomization

[figure not shown]
Baseline (huff-cough only) measurements will be obtained at Visit 2. For visits 3-5, a single ACT method will be employed at each visit, with a randomized order in which the methods are used. We will employ a Latin-square design as shown. First, the 3 periods will be randomized, followed by the sequences (A-C). This will generate a random 3 x 3 table in which each ACT appears once in each row and column. The rows of this table will serve as a block randomization schedule, which will optimize balance for a number of subjects not divisible by the number of possible sequences. Subjects will be assigned to the next row in the table after the baseline visit (repeating the sequences every 3rd subject) to ensure eligibility prior to randomization.

[figure not shown]

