#### **5. Experimental Design and Methods:**

**Key inclusion criteria:** Adults with confirmed diagnosis of cystic fibrosis aged 18 years and older.

**Key exclusion criteria:** Pregnant or lactating women, individuals with severe lung disease (FEV1 <30%), or with exacerbations of lung disease requiring antibiotics or medication change within four weeks prior to enrolment. Individuals unable to use vest-based HFCWO, oscillatory PEP device, or who require oxygen supplementation at rest. We will also exclude individuals with significant balance or gait impairment preventing the individual from tolerating being positioned on a vibrating platform.

**Study design:** Ten (10) adult CF subjects will be recruited from the CF clinic at UNC, and will have a screening visit and four subsequent study visits. At Study Visit 1 huff-cough alone (control) will be performed while the order of the 3 remaining airway clearance therapy (ACT) treatments received at Study Visits 3-5 will be randomized: oscillatory PEP (positive expiratory pressure), high frequency chest wall oscillatory vest, and the vibrating plate device. Only one ACT device will be used at any given visit as adjuncts to huff-coughing, with the same cough regimen used at all study visits (Figures 3 & 4). Study visits will be at least three and no more than 21 days apart. Subjects who are prescribed hypertonic saline, dornase alfa, long-acting bronchodilators, and/or airway clearance will be asked to withhold use of these agents/activities after midnight before each study visit after screening. No bronchodilators will be used as part of this study.

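### Repeating one 3 x 3 Latin square gives each device a single device predecessor, so adjusting for carryover costs about five-fold variance; alternating with the mirror square avoids most of that at no cost

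*Combined protocol and SAP*

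**What the plan says.** The Randomization section states "We will employ a Latin-square design as shown". Periods are shuffled, then sequences, and "This will generate a random 3 x 3 table in which each ACT appears once in each row and column". Then "The rows of this table will serve as a block randomization schedule", with assignment running down the rows and "repeating the sequences every 3 rd subject". The stated reason is balance when the number of subjects is not a multiple of the number of sequences. The printed square has A = Vest-OPEP-WBV, B = WBV-Vest-OPEP and C = OPEP-WBV-Vest.

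Huff-cough alone is outside the square: "Baseline (huff-cough only) measurements will be obtained at Visit 2". On spacing, the Study design paragraph of section 5 says "Study visits will be at least three and no more than 21 days apart". Subjects who are prescribed airway clearance "will be asked to withhold use of these agents/activities after midnight before each study visit after screening".

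The Data analysis section makes each device versus huff-cough on AUC-Clr274 the primary comparison. Its repeated measures model treats subject as a random factor and names no period, sequence or carryover term.

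**The concern.** In the printed square, apart from the first device period, OPEP comes only after Vest, WBV only after OPEP, and Vest only after WBV. Shuffling periods and sequences does not change this: any 3 x 3 Latin square has one device predecessor per device. A residual effect of one device would then fall on one particular other device, and the design holds little information with which to adjust for it.

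The documents give no reason to regard three days as an adequate washout for mucus clearance. What is at stake is the comparison between devices. The Rationale section lists comparing WBV with traditional methods as a purpose, the analysis section compares sputum and biomarker changes across methods, and Specific Aim 4 asks the pilot to inform design features of future trials. Whether a short-gap crossover is sound is such a feature.

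**Working it through.** **The plan's own figure.** The sample size section uses a change of 20.0 with SD 15.1, a paired two-sided t-test and alpha 0.05. d_z = 20.0/15.1 = 1.325 (printed as 1.33, with no effect on n). Exact noncentral-t power is 73.7% at n = 6, 83.0% at n = 7 and 96.0% at n = 10. The stated 7 reproduces. The plan gives no figure for carryover or design efficiency.

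**Predecessors.** There are 12 possible 3 x 3 Latin squares. In all 12 each device has exactly one device predecessor. Of the six column orders of the printed square, three keep its cycle and three give the mirror cycle.

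**Model.** Device sessions only: response = subject + period + device (+ first-order carryover from the previous device) + error with within-subject variance sigma^2. For a contrast k, the variance is k'(X'X)^- k sigma^2. The bias from an unmodelled Vest residual L is k'(X'X)^- X'z L, where z marks the sessions that follow Vest. With n = 10, the single square is used 4/3/3, sequence A four times. The alternated design gives blocks of three to the square, mirror, square, then one mirror row (Vest-WBV-OPEP here) to the tenth subject.

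| n = 10 | Single square | Alternated with mirror |
|---|---|---|
| Bias, OPEP minus Vest | 0.67L | 0.37L |
| Bias, WBV minus OPEP | -0.70L | -0.11L |
| Bias, WBV minus Vest | -0.03L | 0.26L |
| Variance, no carryover terms | 0.202 sigma^2 | 0.202 sigma^2 |
| Variance, carryover terms fitted | 0.98 to 1.09 sigma^2 (mean 1.019) | 0.25 to 0.27 sigma^2 (mean 0.263) |

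The bias rows are without carryover terms. Under alternation WBV minus Vest ranges from 0.23L to 0.29L, depending on the tenth subject's mirror row.

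Variance inflation from adjusting: 1.019/0.202 = 5.0 for the single square and 0.263/0.202 = 1.3 when alternated.

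**Check by counting.** In the single square OPEP follows Vest in sequences A and B, so in 4 + 3 = 7 of 10 subjects. The raw OPEP mean shifts by 0.70L and the other two device means by 0. When alternated, OPEP follows Vest in 4 of 10 and WBV follows Vest in 2 or 3 of 10, giving shifts of 0.4L and 0.2L to 0.3L. These are also the biases against huff-cough. The total is about the same, shared between two devices.

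**On the AUC scale.** This assumes sigma = 15.1/sqrt(2) = 10.68, derived from the plan's SD of change. The standard error of a device-versus-device contrast is 10.68 x sqrt(0.202) = 4.8 unadjusted, 10.68 x sqrt(1.019) = 10.8 adjusted in the single square, and 10.68 x sqrt(0.263) = 5.5 adjusted when alternated. For a 20-unit difference, adjusted power is 41% against 92%. The plan assumes 20 units for a device versus baseline, not between devices, so the power figures are illustrative.

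**The case against.** The strongest reply is that the planned analysis gains nothing from the mirror square alone. No carryover term is specified, the unadjusted variance is 0.202 sigma^2 either way, and alternation moves bias onto WBV minus Vest, which was nearly clean. All of this stands, and it is why the fix needs the sensitivity analysis as well as the allocation change.

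The primary contrast is each device against huff-cough, which is always measured first. A reader might infer that alternation protects the primary result. It does not: residual effects are shared between devices rather than removed, and with free visit effects the contrast with huff-cough cannot be estimated in either design. The Data analysis section also specifies no device-versus-device test on MCC, although the Rationale states that purpose for WBV.

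A reader might also infer that device and carryover effects are inseparable. They are not. In the first device period every device follows huff-cough, and that third of the sessions keeps the adjusted contrasts estimable, at five-fold variance.

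Finally, a reader might infer that three days is too short. No passage shows this. Each exposure is a single day with two 40-minute intervention periods, and prescribed home airway clearance need stop only at midnight before a visit, which makes a device-specific residual from days earlier less plausible. The remark in the sample size section that comparable preliminary data are lacking concerns effect size, not washout.

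A Latin square is a recognised choice for a 10-subject pilot, and its stated reason, balance, is sound. Alternation keeps period balance within every complete block of three.

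**Conclusion.** The point holds as a free design improvement, not as a flaw that invalidates the trial. The repeated square directs any first-order residual onto one device and makes carryover adjustment of device-versus-device contrasts about five times as costly in variance, against about 1.3 times with alternation. The bias figures are multiples of an unknown L, which may be zero. The variance figures assume n = 10 with complete data, additive subject and period effects, and carryover from the preceding device only. At n = 10, which is not a multiple of six, carryover balance under alternation is near rather than exact. The fixed first position of huff-cough is a separate limitation that this change leaves in place.

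**What to change.** In the Randomization section, replace the repetition of one square with alternating blocks of three. The first block uses the rows of the generated square and the next the rows of its mirror (for the printed square: Vest-WBV-OPEP, OPEP-Vest-WBV, WBV-OPEP-Vest), and so on, with row order randomised afresh in each block.

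In the Data analysis section, add a pre-specified sensitivity analysis of the device-versus-device contrasts with period and first-order carryover terms. State there that it does not address the comparison with huff-cough.

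Cost: a revised sentence in each section and a new allocation list. No added subjects, visits or procedures, and no loss of unadjusted precision.

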### Study Visits

The order of procedures at each study visit is outlined in Figure 3. At each visit, subjects will be asked about intercurrent adverse events, changes in medical regimen and health status. Vital signs and a pregnancy test (if applicable) will be performed to ensure subject safety. Spirometry will not be obtained during study visits as the forced expiratory maneuver may stimulate MCC and mediator release (nitric oxide, nucleotides), and therefore may interfere with results. Exhaled breath condensate (EBC) and fraction of exhaled nitric oxide (FENO) samples will be obtained prior to the inhalation of isotope and immediately after the first ACT intervention. Procedures for biomarker collection and analysis are discussed below.

**Figure 3**

Sequence	Period		
	1	2	3
A	Vest	OPEP	WBV
B	WBV	Vest	OPEP
C	OPEP	WBV	Vest

**Figure 4**

### ACT Interventions

ACT interventions will be performed while capturing MCC images, as shown in Figure 4. Each 40-minute intervention period will be broken into six segments of ACT, each followed by a huff-cough maneuver. The protocol for each ACT is discussed below. Each ACT segment will be separated by two minutes of MCC image capture, which will allow quantification of particle clearance using previously described methods. To perform huff-coughs, subjects will be instructed to inspire to about 75% of total lung capacity (TLC), hold inspiration for 2 seconds, and then expire forcefully to near residual volume (RV). This breathing pattern will be repeated two additional times and followed by a single, forceful cough to complete a single huff-cough maneuver. During each of the six segments of the intervention period, there will be five minutes for transitioning from image capture to ACT, completion of the ACT, performing huff-cough, and repositioning in front of gamma camera. Four minutes are allotted for ACT and 1 minute total time for transitions and huff-cough. During the baseline visit, cough clearance will be performed during time allotted for huff-coughs but no additional interventions will take place during the 4-minute time for ACT. Immediately following the intervention period, additional EBC and FeNO will be obtained, and the subject will again be positioned in front of the camera for an additional 48 minutes of image capture.

### Second Intervention Period

By repeating the visit-specific ACT intervention on the same study day (16 min and 196 minutes after isotope inhalation) we hope to identify the optimal timing of sputum volume and MCC measurements to differentiate the effects of the different ACT modalities. After the initial ACT intervention and MCC assessment, subjects will remain within the Marsico Clinical Research Center and will refrain from any inhaled medications, vigorous exercise, or additional ACT during this time. 180 minutes after inhalation of tracer, a repeat image capture and intervention period will occur identical to the first. This will conclude the study visit day.

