**Hypothesis 1:** *Device-assisted airway clearance therapy using OPEP, HFCWO-vest, and whole-body vibration causes a demonstrable increase in MCC and expectorated sputum volume when compared to cough alone.*

**Hypothesis 2:** *Airway signaling molecules, including NO and purine nucleotides (e.g. ATP, adenosine), are associated with the regulation of MCC and mediate the increase in mucus clearance that occurs following the application of mechanical stimuli from OPEP, HFCWO-vest, and whole-body vibration.*

We will test these hypotheses through these specific aims:

**Specific Aim 1:** Measure the effects of 4 different ACT modalities on MCC, using gamma scintigraphy.

**Specific Aim 2:** Measure the effects of different ACT modalities on proposed regulators of MCC, including nucleotide levels (via exhaled breath condensate collection) and exhaled NO.

**Specific Aim 3:** Examine associations between biomarkers of airway mechanical stimulation and measured MCC.

**Specific Aim 4:** Determine what study characteristics would be needed to more fully assess the effectiveness of ACTs, including sample size, study design features, and outcome measures.

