### ***Outcome Measures***

#### *Mucociliary Clearance*

Background and transmission scans will be performed per the MCC Standard Operating Procedure (see attachment) to subtract background radiation levels and allow identification of lung boundaries and regions of interest. The Tc-99 sulphur colloid radiotracer will be inhaled using our slow inhalation, large particle method. The subject will be positioned in front of the gamma camera, and images will be obtained for 16 minutes prior to any intervention. Sixteen minutes after particle inhalation, there will be a 40-minute intervention period with whichever ACT the subject is to receive during that study visit. Following the ACT period, there will be an additional 38 minutes of image capture. After an 86-minute break (i.e. 180 minutes after tracer inhalation), an identical MCC image capture period with ACT intervention will occur (Figure 3).

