## Data analysis:

[name], biostatistician for the UNC CF Center, has been closely involved in the study design and will be responsible for overseeing the database creation and management, as well as performing final statistical computations during data analysis.

**Primary comparison:** MCC will be visualized using a whole right lung clearance vs. time plot from immediately after isotope inhalation through 274 minutes post-inhalation. The area under this curve (AUC-Clr274), will be used to reflect “total clearance”, and will serve as the primary outcome of this study. We will compare AUC-Clr274 in huff-cough alone to AUC-Clr274 measured with each of the ACT modalities (HFCWO-vest, OPEP device, and WBV device).

**Secondary comparisons:** AUC-Clr over other intervals (i.e. 94 min and 180 min), and from other lung regions of interest (i.e. peripheral and central lung zones) will be calculated and compared in similar fashion as above. Furthermore, the change in the rate of clearance (represented by the slope of the MCC curve,  $d\text{Clr}/dt$ ) before (0-16 minutes of MCC curve;  $d\text{Clr}/dt_{0-16}$ ) versus during/after the initial ACT intervention (16 – 56 minutes;  $d\text{Clr}/dt_{16-56}$ ) will be used to compare the immediate effects of each ACT versus. huff coughs alone. The mean changes in EBC purines concentrations and FeNO, (before vs. after ACT) will be calculated. If these are found to be different from zero, a comparison between huff-cough alone and each of the ACT modalities will be made. Total sputum weights and % solids at baseline and after each ACT 40 minute period will be compared across each of the ACT modalities. We will also assess for a relationship between changes in EBC measurements, FeNO, and changes in MCC.

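### No planned MCC measure estimates the second ACT session separately, although that session is repeated partly to find the best timing for MCC measurement

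*Combined protocol and SAP*

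**What the plan says.** **Purpose.** The Second Intervention Period section repeats the visit's ACT ("16 min and 196 minutes after isotope inhalation") and gives the reason: "we hope to identify the optimal timing of sputum volume and MCC measurements to differentiate the effects of the different ACT modalities". Specific Aim 4 is to "Determine what study characteristics would be needed to more fully assess the effectiveness of ACTs, including sample size, study design features, and outcome measures".

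**Schedule.** Under Mucociliary Clearance: "Sixteen minutes after particle inhalation, there will be a 40-minute intervention period", then 38 minutes of further imaging. "After an 86-minute break (i.e. 180 minutes after tracer inhalation), an identical MCC image capture period with ACT intervention will occur".

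**MCC analyses (Data analysis section).**
- Primary: area under the "whole right lung clearance vs. time plot from immediately after isotope inhalation through 274 minutes post-inhalation" (AUC-Clr274), each ACT against huff-cough alone.
- Secondary: "AUC-Clr over other intervals (i.e. 94 min and 180 min), and from other lung regions of interest". No start times are written for these windows.
- Secondary: one change in slope, 0-16 against 16-56 minutes, which "will be used to compare the immediate effects of each ACT versus. huff coughs alone". It is tied to the initial intervention.

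A repeated measures model with subject as a random factor is named. It has no session term and no session-by-modality contrast. Sputum weight and percent solids, by contrast, are to be compared after each 40-minute ACT period, so the sputum half of the timing aim already has a per-session analysis.

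**The concern.** The second session produces a full set of images at every visit: 180-196 minutes before the ACT, 196-236 during it and 236-274 after it. The section on the second session gives timing as the reason for repeating the ACT, yet none of the listed MCC contrasts uses these images on their own. The clearance curve is cumulative, so any area that starts at time 0 carries the first session's gain through the second.

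At stake is one stated purpose of the repetition. From the planned outputs, a reader could not tell how much of a difference in AUC-Clr274 arose in the second session, or whether imaging around that session separates the devices better or worse than imaging around the first. The point concerns MCC only.

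**Working it through.** **1. Reproduce the plan's time marks.** From the Mucociliary Clearance section: 16 + 40 + 38 = 94; 94 + 86 = 180; 180 + 16 = 196; 196 + 40 = 236; 236 + 38 = 274. These match 94, 180, 196 and 274. (The ACT Interventions section gives 48 rather than 38 minutes of imaging after the first session. That would give 104 and 190, so only 38 fits, and the two sections should be reconciled.)

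**2. Which planned MCC measures reach the second session (196-236)?**

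| Measure | Window (min) | Contains session 2? |
|---|---|---|
| Slope contrast | 0-16 vs 16-56 | No |
| AUC-Clr94 | 0-94 (start inferred) | No |
| AUC-Clr180 | 0-180 (start inferred) | No |
| AUC-Clr274 | 0-274 (start stated) | Yes, mixed with session 1 |

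**3. Weight of each session in AUC-Clr274.** Let D be the extra cumulative clearance, ACT minus huff-cough, gained in one session. Assume that it accrues linearly from s to e and is held to T. Its area is D × [(e − s)/2 + (T − e)].
- Session 1 (16, 56, 274): D × (20 + 218) = 238D.
- Session 2 (196, 236, 274): D × (20 + 38) = 58D.
- Ratio 238/58 = 4.1. Session-2 share 58/296 = 19.6%.

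**4. Vary the assumptions.**
- The session-1 gain fades linearly to zero by 274 (huff-cough catches up) and the session-2 gain is held. Session 1 adds D × (20 + 218/2) = 129D. Session-2 share 58/187 = 31%.
- Session 2 gains 2D and session 1 is held: 116/(238 + 116) = 33%.

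**5. Does subtracting AUC-Clr180 from AUC-Clr274 isolate session 2?**
- Session-1 gain held: 180-274 contains 94D from session 1 and 58D from session 2, so 94/152 = 62% is session-1 carry-over.
- Session-1 gain fading: the advantage left at 180 is 94/218 = 0.431D. It adds 0.431D × 94/2 = 20.3D, which is 20.3/78.3 = 26%.

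Subtraction leaves carry-over in both cases.

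**6. What would session-2 measures pick up?**
- Area over 180-274 re-zeroed at 180, as a fraction of initial activity: 58D if the session-1 gain is held, the same weight that session 1 has in AUC-Clr94 (20 + 38 = 58). If that gain is fading, 58D − 20.3D = 37.7D.
- Slope over 196-236 minus slope over 180-196: D/40 per minute in both cases, because a linear fade affects both slopes equally.

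The re-zeroed area therefore still depends on what session 1 did, and must be reported with that caveat.

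**7. Sample size.** With dz = 20.0/15.1 = 1.32 (plan: 1.33), a paired two-sided t-test at 0.05 has power 0.74 with 6 subjects and 0.83 with 7. The plan's 7 reproduces, and nothing above changes it.

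**The case against.** The best defence is that the second session is not ignored. It lies inside the primary outcome, which is compared for every ACT. The stated goal is also when to measure, not what the second session does by itself. Windows closing at 94, 180 and 274 minutes fall after the first imaging block, just before the second and after it, so comparing the device differences across them bears on that goal. The curve is plotted to 274 minutes, and means, SDs and 95% CIs are promised for MCC parameters. This is a ten-subject pilot that only hopes to learn about timing, and the images will exist for exploratory work.

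Much of this stands. A reader might infer that the second session's effect is never estimated, or that the plan cannot address timing at all. Neither follows: the effect is estimated in combination, and the three windows give partial information. What they cannot do is attribute a difference to the second session, because of the carry-over. Leaving the contrast until the data are seen, with ten subjects, three devices and several possible windows, invites choosing the best-looking one.

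Two objections to the remedy also stand. Activity remaining at 180 minutes is a post-treatment quantity: a device that clears well early leaves less to clear later. The same ACT is given in both sessions, so timing and depletion cannot be separated by any analysis. And choosing the session with the larger standardised difference means choosing the larger of two noisy estimates.

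**Conclusion.** The concern holds in this form: no planned MCC measure estimates the second session separately, although finding the best timing for MCC measurement is a stated reason for repeating the ACT. The second session supplies none of AUC-Clr94, AUC-Clr180 (both read from time 0) or the slope contrast. With equal gains it supplies about 20% of the AUC-Clr274 difference if the first-session gain is held, and about 31% if that gain fades linearly to zero by 274 minutes. The documents support neither scenario over the other, so these shares are illustrations.

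Four stronger readings go too far.
- That every AUC starts at time 0: this is written only for the primary. It is the natural reading for the others.
- That imaging runs to 274 minutes solely for the second session: the background on the slow-inhalation method places small-airway clearance between 90 minutes and 6 hours, a separate ground for late imaging.
- That Aim 4 fails: it names sample size, design features and outcome measures, not imaging times.
- That a device acting mainly in the second session would be missed: this needs an effect pattern and an SD that the documents do not give.

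The gap is secondary and exploratory. It merits correction because a stated purpose lacks a matching analysis.

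**What to change.** In the Data analysis section:

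1. Write start and end times for every AUC.
2. Add two exploratory secondary outcomes, each ACT versus huff-cough in the existing repeated measures model:
   - the change in slope, dClr/dt(196-236) − dClr/dt(180-196);
   - clearance over 180-274 minutes re-zeroed at 180, shown both as a fraction of initial activity and as a fraction of activity remaining at 180.
3. Report both with 95% CIs beside the first-session equivalents: the 16-56 minus 0-16 slope change and AUC-Clr94.
4. State that second-session results are conditional on what the same ACT cleared in the first session, and that the design cannot separate timing from depletion.
5. Do not base the timing recommendation solely on which session shows the larger standardised difference.

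The cost is a few lines of text and a little computation on images already planned, with no added imaging, procedures or subjects. The downside is two more exploratory contrasts per device. The primary comparison and sample size do not change.
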